7.5.7 Pharmacodynamic assessments

7.5.7.1 Heparan sulfate

7.5.7.1.1 Heparan sulfate in serum and CSF

Blood (0.3 mL) is collected at Baseline and pre-infusion at Weeks 2 to 4, 8, 12, and 24, and if applicable at Early Termination of SOBI003 treatment, for analysis of HS in serum. In addition, serum is also collected on Day 2 at Weeks 12 and 24.

CSF (0.2 mL) is collected at Baseline and at Weeks 12 and 24 for analyses of HS.

The HS analyses are performed at a central laboratory (York Bioanalytical Solutions Limited, [name]). The HS polymer itself is highly heterogeneous and therefore it is not possible to analyze at the intact molecule level. The detection of HS levels is initiated by depolymerization of the polymer mixture enzymatically, followed by analysis of the constituent disaccharides (22). The polymer mixture includes the HS polymer as well as accumulated intermediate HS degradation products. Throughout this protocol, the term “HS” is used for the assessed disaccharide levels.

Effects of SOBI003 on HS storage in affected cells are assessed by measuring HS in serum and CSF using liquid chromatography tandem mass spectrometry (LC-MS/MS). The total level of HS is measured by analyzing selected disaccharides derived from enzymatic digestion (adaptation of method described in Naimy et al. 2016 [22]).

Sampling, storage and shipment details are provided separately in the study-specific Laboratory Manual.

7.5.7.1.2 Heparan sulfate in urine

Urine (3 mL) samples are collected at Screening, Baseline, and pre-infusion at Weeks 2 to 4, 8, 12 and 24, and if applicable, at Early Termination of SOBI003 treatment, for analysis of HS. In addition, urine is also collected on Day 2 at Weeks 12 and 24.

The urine HS analyses are performed at a central laboratory (Greenwood Genetic Center, [name]). HS is quantified using stable isotope dilution-tandem mass spectrometry. The urine sample is treated with methanol to produce HS polymer dimers that are separated by ultra-performance liquid chromatography (UPLC) and analyzed by electrospray ionization tandem mass spectrometry (MS/MS). The assay reports the concentration of HS relative to the creatinine concentration in the urine.

Sampling, storage and shipment details are provided separately in the study-specific Laboratory Manual.

7.5.7.2 Future bioanalytical research

As local regulations permit and provided that additional separate caregiver consent is given, blood, urine and CSF samples are collected for future analyses. At Baseline, blood (2 mL), urine (2 mL) and CSF (1 mL) samples are collected for future biomarker analyses. At Week 22, blood and urine are collected for future biomarker analyses and additional blood (2 mL) is collected for future genetic research. At Week 24, CSF is collected for future biomarker analyses.

When possible, the baseline blood sample should be collected at least 4 weeks prior to the planned start of SOBI003 infusion in order to minimize the total blood volume drawn within one-month timeframes.

The samples will be stored at a central laboratory (York Bioanalytical Solutions Limited, [name]) for a maximum of 10 years following study completion (i.e., last patient's last visit in this study).

MPS IIIA is a very rare and severe disease for which there is a lot of research ongoing to further increase the understanding of disease pathology as well as diagnosis. The purpose of the sample storage is to allow future exploration/confirmation of new research findings. This includes:

- SGSH genotypes
- Geno- and/or phenotype associated correlations with possible impact on safety, tolerability, immunogenicity, PK and PD related to SOBI003 treatment
- Biomarkers in serum, urine and/or CSF with possible relation to the safety, tolerability, immunogenicity, PK and PD of SOBI003

The results of any such analyses will not be included in the Clinical Study Report for this study, but reported separately when analyzed, thus enabling exploration of any emerging novel disease-related discoveries of e.g., previously unknown disease alleles, inflammatory cytokines (e.g., IL1Ra, TNF α , calprotectin, neopterin), other HS biomarkers (e.g. HS metabolites), components of the complement system, and neurodegeneration (e.g., T-tau, hepatocyte growth factor, calbindin D).

Sampling details are provided separately in the study-specific Laboratory Manual.

7.5.7.3 Appropriateness of measurements

Storage of HS in brain lysosomes causes pathological changes such as neuroinflammation and inhibition of autophagy in the MPS IIIA mouse model (23). As demonstrated in nonclinical studies, SOBI003 treatment reduces blood and brain HS levels, has favorable effects on pathophysiological parameters such as neuroinflammation and lysosomal size and shows trends towards normalization of behavior in mice. Furthermore, the levels of HS derivatives in brain homogenate and CSF are strongly correlated, and the HS reduction at different dose levels of SOBI003 is paralleled in these two compartments.

Patients with MPS IIIA have elevated CSF HS levels in CSF as compared to healthy individuals (24). Also in humans, a reduction of HS in CSF is expected to mirror the reduction in brain and thus be a useful PD tool for dose selection.

8 Quality control and quality assurance

This study will be conducted in compliance with this protocol, study specific procedures, INC Research SOPs, the ICH Guideline for Good Clinical Practice, and applicable regulatory requirements.

Monitoring visits to the study site are performed periodically during the study, to help ensure compliance with the protocol, study specific procedures and applicable regulatory requirements. Source documents are reviewed for verification of agreement with data in CRFs. All patient informed consent forms are reviewed. The investigator or institution guarantees access to source documents by Sobi, its representatives, and appropriate regulatory agencies.

The study site may be subject to a quality assurance audit by Sobi or its representatives, as well as inspection by appropriate regulatory agencies.

It is important that the investigator(s) and the(ir) relevant personnel are available during the monitoring visits and possible audits and that sufficient time is devoted to the process.

9 Statistical plan

9.1 Determination of sample size

Given that this is a first-in-human study and with no formal hypothesis tests, no sample size calculation has been performed. Three sequential dose levels with 3 patients in each cohort has been evaluated to be sufficient to allow assessment of safety and tolerability concerns, as well as characterize a PD dose-response relationship in this rare population with a high unmet medical need.

9.2 Definition of study populations

The following analysis sets will be used in the statistical analyses.

Safety set (SAF): The SAF will consist of all patients who received at least 1 dose of IMP.

Full-analysis set (FAS): The FAS is the efficacy analysis set and will consist of all patients who have a baseline and at least 1 post baseline assessment of any secondary or exploratory assessment.

PK analysis set (PK): This PK set will comprise patients where at least one SOBI003 dose has been administered correctly and where SOBI003 serum or CSF concentration data is available without any protocol deviation interfering with these results.

The SAF is used for the safety analysis, the FAS is used for the secondary and explorative efficacy variables.

Patients in this study who are up to 30 months of age and was initially assigned a dose at least as high as the dose selected for a planned phase III study will be included in a future primary analysis population for demonstrating efficacy. Efficacy will be evaluated using combined data from the FIH study and the extension study, a planned Phase III trial and the corresponding patients in a recent NH study (24), the latter serving as control patients and consisting of the 5 patients with a rapid progressive MPS IIIA disease and a baseline age of 12 to 30 months.

9.3 Overall statistical and analytical plan

9.3.1 General statistical issues

A detailed description of the statistical analyses to be performed will be documented in a statistical analysis plan to be completed prior to database lock.

9.3.2 Demographics and baseline characteristics

Demographic and other baseline characteristics are listed and summarized with descriptive statistics.

9.3.3 Analysis related to primary objective

Safety tabulations of adverse event data, vital signs data, and laboratory data are performed. Continuous variables are summarized using the number of patients, the mean, the standard deviation, the median, the minimum value, and the maximum value. Categorical variables are summarized using frequency counts and percentages.

9.3.4 Analysis related to secondary objective

PK results are presented by dose level using descriptive statistics. In addition, results are presented by demographic characteristics, e.g., age-group and bodyweight, as applicable.

Immunogenicity is summarized using frequency counts and percentages by dose level.

To assess the PD effect of different dose levels of SOBI003 on HS levels in CSF, serum, and urine, linear mixed models are used to model the change from baseline in HS levels as dependent variable, for both logged HS levels and untransformed HS levels, and baseline level and age as continuous covariates, and dose and sex as factors. The analyses are conducted for each assessment time point: Weeks 12 and 24 for CSF, and Weeks 4, 8, 12 and 24 for serum and urine.

In addition, linear mixed analyses with HS levels, both logged HS levels and untransformed HS levels, in CSF serum, and urine, as dependent variable, and baseline level and age as continuous covariates, and dose and sex as factors will be performed across all assessments, with assessment as a repeated factor in a accumulating pattern: across weeks 12 and 24 for HS in CSF, and across Weeks 4 and 8, across Weeks 4, 8 and 12, and across Weeks 4, 8, 12 and 24 for HS in serum.

Endpoints relating to the neurocognition, adaptive behavior, gray matter volume and Quality of Life are summarized using descriptive statistics.

9.3.5 Analysis related to exploratory objectives

Continuous variables are summarized using the number of patients, the mean, the standard deviation, the median, the minimum value, and the maximum value. Categorical variables are summarized using frequency counts and percentages.

9.3.6 Analysis of safety and tolerability data

9.3.6.1 Adverse events

Reported AE(s) during the study are coded using MedDRA and severity of AEs is graded using NCI CTCAE v.03. The number of patients with any AE are summarized in frequency tables by treatment dose level, body system, preferred term, relation to IMP and maximum severity. Listings of AE subgroups such as SAE(s) and adverse events leading to discontinuation are also presented.

9.3.7 Interim analysis

No interim analysis is planned for this 24-week study.

9.3.8 Multiple comparison/multiplicity

Since no hypothesis tests will be performed, there will be no adjustments for multiplicity.

9.3.9 Handling of missing data

No imputation for missing data will be used.

10 Data collection, handling and record keeping

10.1 Data standards

Collection of data should be performed in the Clinical Data Acquisition Standards Harmonization (CDASH) format, according to the Clinical Data Interchange Standards Consortium (CDISC). The standards should be used to the extent possible and/or required for the specific study/project. The minimum requirement of the CDISC standard is to collect all core variables specified as 'Required' in the Study Data Tabulation Model (SDTM) format.

10.2 Case report form

A CRF is required and should be completed for each included patient. In this study an electronic CRF will be used. The completed original CRFs are the sole property of Sobi and should not be made available in any form to third parties, except for authorized representatives of appropriate regulatory authorities, without written permission from Sobi.

It is the responsibility of the investigator to ensure completion and to review and approve all CRFs. CRFs must be signed electronically by the investigator. These signatures serve to attest that the information contained on these CRFs is correct. At all times, the investigator has final responsibility for the accuracy and authenticity of all clinical and laboratory data entered on the CRFs.

10.3 Source data

Patient source documents are the physician's patient records maintained at the study site. In most cases, the source documents will be the hospital's or the physician's chart. In those cases, the information collected on the CRFs must match those charts. In addition to the physician's patient records, the printed 12-lead ECGs are source. For the MRIs and actigraph assessments, the digital files are the source. For the VABS-II, BSID-III and the KABC-II, the completed test forms and the central reader's confirmation of total scores and age-equivalence scores are the source.

10.4 Database closure

Prior to database closure, all tasks or criteria defined in the data management plan must be completed and documented. The study database must be locked before generation of any final results. The database lock will be approved by relevant study personnel and all edit accesses will be removed. The study database can only be unlocked in case critical errors, affecting the main conclusions of the study, are discovered.

10.5 Record retention

To enable evaluations and/or audits from Health Authorities and/or Sobi (or delegates), the investigator agrees to keep records in accordance with the essential documents defined in the ICH GCP Guidelines [1], including the identity of all participating patients (sufficient information to link records, e.g., CRFs and hospital records), all original signed informed consent forms, copies of all paper CRFs (i.e., completed paper questionnaires and BSID-III/KABC-II assessments forms), an archival copy on compact disc of the electronic CRFs provided by INC Research and detailed records of IMP accountability. The records should be retained by the investigator according to local regulations or as specified in the Clinical Trial Agreement.

If the investigator relocates, retires, or for any reason withdraws from the study, the study records may be transferred to an acceptable designee, such as another investigator, another institution, or to Sobi. The investigator must obtain Sobi's written permission before disposing of any records.

11 End of study

The end of this study is defined as the date of last patient out, i.e., the last patient's last visit.

12 Sponsor's discontinuation criteria

Sobi reserves the right to discontinue the study prior to inclusion of the intended number of patients, but intends only to exercise this right for valid scientific or administrative reasons. After such a decision, the investigator must contact all participating patients within 2 weeks. All study materials must be collected and all the CRFs completed to the greatest extent possible.

13 Dissemination and publication of results

Sobi will register the study and post study results regardless of outcome on a publicly accessible website in accordance with applicable laws and regulations, e.g. on www.clinicaltrials.gov and EudraCT.

For this rare indication, patients enrolled in this Phase I/II study may form part of the pivotal efficacy population by continuation into the extension study. Cognition is the primary efficacy outcome in MPS IIIA, therefore the cognition and adaptive behavior results at Week 24 of this

Phase I/II study may be withheld from publishing in order to prevent the risk of inadvertent bias of cognition and adaptive behavior assessments in the extension study.

Appendix 1 Blood sampling volume overview

Table 12 Blood sampling volumes (mL) per study visit

Sample	SA, SGSH genotype	Acute reactions	Safety	Immuno-genicity	HS	Pharmacokinetics ^a			Future research	Total blood volume (mL)		
Week						BW ≥20 kg	BW 15 to <20 kg	BW 10 to <15 kg		BW ≥20 kg	BW 15 to <20 kg	BW 10 to <15 kg
-12 to -7	5,0		3,7			0,3	0,3	0,3		9,0	9	9
-6 to -2		6,4							2	8,4	8,4	8,4
-1				1,5	0,3	0,3	0,3	0,3		2,1	2,1	2,1
1			7,4			3,3	1,8	0,6		10,7	9,2	8
2			7,4	1,5	0,3	0,9	0,9	0,3		10,1	10,1	9,5
3			7,4 ^b		0,3	0,9	0,9	0		8,6	8,6	4
4			3,7	1,5	0,3	3,6	3,6	1,8		9,1	9,1	7,3
5			3,7			0,3	0,3	0,3		4	4	4
6			3,7							3,7	3,7	3,7
7			3,7							3,7	3,7	3,7
8			3,7	1,5	0,3	0,9	0,9	0,9		6,4	6,4	6,4
10			3,7							3,7	3,7	3,7
12			3,7	1,5	0,6	3,6	3,6	1,8		9,4	9,4	7,6
13						0,3	0,3	0,3		0,3	0,3	0,3
14			3,7							3,7	3,7	3,7
16			3,7							3,7	3,7	3,7
18			3,7							3,7	3,7	3,7
20			3,7							3,7	3,7	3,7
22			3,7						4,0	7,7	7,7	7,7
24			3,7	1,5	0,6	3,9	3,9	2,1		9,7	9,7	7,9

a 168 h samples are counted to the following week, except for week 24

b In children with a body weight < 15 kg, the volume will be 3,7 mL, since no safety sample will be collected on Day 3 of Week 3

Table 13 Blood sampling volumes (mL) per 4-week study periods

Sample	SA, SGSH genotype	Acute reactions	Safety	Immuno-genicity	HS	Pharmacokinetics ^a			Future research	Total blood volume (mL)		
Week						BW ≥20 kg	BW 15 to <20 kg	BW 10 to <15 kg		BW ≥20 kg	BW 15 to <20 kg	BW 10 to <15 kg
-1 to 3			22,2 ^b	3	0,9	5,4	3,9	1,2	0	31,5	30	23,6
4 to 7			14,8	1,5	0,3	3,9	3,9	2,1	0	20,5	20,5	18,7
8 to 11			7,4	1,5	0,3	0,9	0,9	0,9	0	10,1	10,1	10,1
12 to 15			7,4	1,5	0,6	3,9	3,9	2,1	0	13,4	13,4	11,6
16 to 19			7,4	0	0	0	0	0	0	7,4	7,4	7,4
20 to 23			7,4	0	0	0	0	0	4	11,4	11,4	11,4
Total			66,6^c	7,5^c	2,1^c	14,1^c	12,6^c	6,3^c	4^c	121,4^d	119,9^d	108,1^d

a 168 h samples are counted to the following week, except for week 24

b In children with a body weight < 15 kg, the volume will be 18,5 mL, since no safety sample will be collected on Day 3 of Week 3

c From -1 to Week 23

d Total study = Week -12 to Week 24

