The screening visit can be performed up to 12 weeks prior to the first SOBI003 infusion. At the screening visit, the MPS IIIA diagnosis is verified and the genotype is determined at a central laboratory (see Section 7.5.2.1). To determine the patient's developmental age, the VABS-II is assessed by interviewing the patient's parent/caregiver and the mean of the subdomain age-equivalence scores is determined. Once the patient eligibility has been confirmed, visits are scheduled for baseline assessments and insertion of a central venous access port (see Section 7.5.1.3). The baseline assessments and procedures should be performed within 6 weeks prior to the first SOBI003 infusion. There should however be at least 2 weeks between the insertion of the venous access port and the first SOBI003 infusion, and the VABS-II and BSID-III/KABC-II should be assessed within 2 weeks prior to the first SOBI003 infusion. The total study duration for an individual patient will range from 31 to 36 weeks.

Patients are assigned to a dose cohort in consecutive order as the eligibility criteria have been confirmed, with prioritization of the younger patients. There is thus no restriction or requirement regarding the site distribution of patients per cohort, i.e., patients within one cohort can be recruited at only one site or at multiple sites.

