7.2 Discussion of study design

Regulatory advice on the design of the Phase I/II study was obtained from the FDA on 21 June 2017.

The non-controlled design of the FIH study is justified by the MPS IIIA disease severity, rapid progression, lack of available treatment and the limited number of potential patients for study participation.

Three sequential dose levels with 3 patients in each cohort will enable assessment of safety and tolerability, as well as characterize a pharmacodynamic dose-response relationship.

A study duration of 24 weeks has been chosen to enable establishment of a dose-response relation in terms of reduction of HS in CSF.

Patients between 1 and 6 years of age who have not received previous treatment for MPS IIIA with an ERT, gene- or stem cell therapy will be eligible to participate in this study. Patients carrying the S298P mutation, a mutation that is associated with a slower progression of disease, will be excluded to reduce the variability in HS levels in CSF.

Patients below 1 year are considered more vulnerable and it would be preferable to initiate inclusion of such patients after the safety of SOBI003 has been established in older patients. In addition, the lower age limit of 1 year has been selected to reduce the potential variability in SOBI003 PK and to ensure that the blood sampling volumes needed for the Phase I/II study can be collected. Applying the European Commission guidance (20), the study-related blood loss should not exceed 3% of the total blood volume during a period of 4 weeks and should not exceed 1% at any single time. In an average 1 year-old child with a bodyweight of 10 kg, it is thus considered acceptable to draw blood volumes of 8 mL as a single draw and 24 mL over a 4-week period, assuming an estimated blood volume of 80 mL/kg. These volumes are considered appropriate to adequately monitor safety and to generate data enabling conclusions on PK and PD. The upper age limit of 6 years has been selected to exclude patients that are close to progressing or who have progressed to a more severe state of disease which might interfere with protocol compliance.

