- k Use of general anesthesia or sedation is per local hospital routine and anesthesiologist judgement, as well as selection of anesthetic/sedative agents. If all Baseline procedures are not completed in one session, then local hospital routine determines minimum time between consecutive anesthetic/sedation episodes.
- l The port should be inserted at least 2 weeks prior to first SOBI003 infusion.
- m Only applicable when separate consent has been provided for future research. At Week 22, blood is collected for future genetic research. At Baseline and Week 22, blood and urine are collected for future biomarker research. CSF is collected at Baseline and Week 24 for future biomarker research. In case of Early Termination of SOBI003 treatment, blood and urine is collected for storage for future biomarker and genetic research.
- n Central laboratory analyses of sulfamidase activity in leucocytes.
- o Sampling time points:
 - Weeks 1 to 3: pre-infusion (Day 1) and Day 3. For patients <15 kg body weight, blood sampling on Day 3 at Week 3 is NOT applicable.
 - Weeks 4 to 8: pre-infusion.
 - Weeks 10 to 22: biweekly pre-infusion, i.e., Weeks 10, 12, 14 etc.
 - Week 24: Day 3.
- p Blood sampling for only hsCRP, IL-1ra, TNF α , IgE, and tryptase. Baseline sample analyzed only in case acute infusion/anaphylactic reaction occur during SOBI003 treatment to facilitate the determination of reaction etiology.
- q Frequent PK blood sampling is conducted at Weeks 1, 4, 12, and 24. Samples are also collected before start of infusion and at completion of the infusion at weeks 2, 3 and 8. PK blood sampling will be adjusted based on the patient's bodyweight in order not to exceed blood draw volume limits. At Baseline, the PK and immunogenicity samples should be taken on the day of CSF sampling for HS analysis. Details on PK blood sampling are given in Table 6.
- r Sleep pattern is assessed by actigraph recordings for 7 consecutive days at Baseline and at Weeks 11-12 and 23-24, i.e., Baseline assessment should preferably be completed prior to any anesthetic/sedation is applied and prior to PK and HS blood samplings. At Weeks 11 and 23, the aim should be to have the recordings completed prior to the SOBI003 infusions on Day 1 at Weeks 12 and 24. A sleep diary is completed during the days of actigraphy. Parents should complete the CSHQ upon completion of each actigraph assessment (i.e., at Weeks 12 and 24 this will be during the infusion days).

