7.5.1.14 Estimated blood sampling volumes and sampling priority list

Applying the European Commission guidance (20), the study-related blood loss should not exceed 3% of the total blood volume during a period of 4 weeks and should not exceed 1% at any single time. Examples of recommended blood draw volume limits per the European Commission guidance are provided in Table 7.

Local and/or regional guidelines regarding blood draw volumes may also apply.

Information of blood volumes per assessment type and sampling occasion are provided in a separate study-specific Laboratory Manual. An overview is presented in Appendix 1.

Blood sampling necessary for the clinical management of the patient will prevail over any study specific sampling.

Should the blood volume be restricted at any of the sampling time points, then the analyses should be prioritized in the following order:

1. Immunogenicity (ADA)
2. Coagulation
3. PK
4. Hematology
5. Blood chemistry
6. HS
7. Blood sample collection for future pharmacogenetics research
8. Serum collection for future biomarker analyses

Table 7 Examples of recommended blood draw volume limits

Patient Weight (kg)	Blood Draw Limits (mL) ^(a)	
	Single Occasion ^(b)	4 weeks ^(c)
10.0	8.0	24.0
15.0	12.0	36.0
20.0	16.0	48.0
25.0	20.0	60.0

a European Commission guidance (20)

b Representing 1% of total blood volume, where total blood volume is estimated to 80 ml/kg body weight

c Representing 3% of total blood volume, where total blood volume is estimated to 80 ml/kg body weight

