7.5.6 Pharmacokinetic assessments

7.5.6.1 Sampling procedures

The sampling procedures are briefly described below and are described in more detail in the study-specific Laboratory Manual. Blood samples are obtained through the central venous access port from the Baseline visit onwards to characterize SOBI003 PK in serum. Separate blood samples from a peripheral venous line are collected in parallel for samples (marked with * below) in order to compare serum SOBI003 concentrations in samples collected from a peripheral line with samples from the central venous access port line, which is used also for the i.v. administration of SOBI003. The purpose of these parallel samples is to confirm that the SOBI003 i.v. infusion does not interfere with the blood sampling. A blood volume of 0.3 mL will be collected from the central venous access port and an additional 0.3 mL blood will be collected from the peripheral venous line when applicable. Duplicate serum aliquots will be prepared at all sampling time points to allow for re-analysis if needed.

Serum samples are collected at Screening and Baseline. Thereafter, frequent sampling is conducted at Weeks 1, 4, 12, and 24 at the following time points: 4 h* (end of infusion), 6*, 12*, 24*, 48, 96, 120 and 168 h after start of infusion. In addition, samples are collected before start of infusion and at completion of the infusion at Weeks 2, 3 and 8. In case SOBI003 infusion is prolonged, PK sampling time points will be adjusted. PK samples will be collected 2 h and 8 h after end of infusion and thereafter 24 h after start of infusion, and thereafter as for the ordinary PK-sampling schedule for the 4 h infusion. A reduced PK blood sampling schedule is applied for patients with low bodyweight to avoid exceeding blood draw volume limits. Details on PK blood sampling are given in Table 6. Acceptable deviations from these planned sampling time points are: 4 h (end of infusion) (+0.5h), 6 (\pm 0.5h), 12 (\pm 0.5h), 24 (\pm 0.5h), 48 (\pm 0.5h), 96 (\pm 1h), 120 (\pm 1h) and 168 (- 1h).

CSF samples (0.5 mL) are collected during general anesthesia at Baseline and at Weeks 12 and 24 for determination of SOBI003. Triplicate aliquots are required for each sampling time-point. At the time of CSF sample collection, a blood sample will also be collected for determination of SOBI003 in serum. In case the time point for the CSF sample is deviating from the planned time-point, the blood sampling should be adjusted accordingly.

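### Appendix 1's fixed 4-week blocks hide the heaviest blood-draw window: Weeks 1-4 total 28.8 mL at 10 to <15 kg, above the protocol's own 3% limit below 12 kg

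*Protocol*

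**What the plan says.** Protocol 7.5.1.14 sets the rule that "the study-related blood loss should not exceed 3% of the total blood volume during a period of 4 weeks", with blood volume taken as 80 mL/kg. Section 7.2 applies it to the child used to justify the lower age limit: "In an average 1 year-old child with a bodyweight of 10 kg", the acceptable volume is "24 mL over a 4-week period, assuming an estimated blood volume of 80 mL/kg".

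Two provisions address light children. Table 3, footnote q, says "PK blood sampling will be adjusted based on the patient's bodyweight in order not to exceed blood draw volume limits", and 7.5.6.1 says "A reduced PK blood sampling schedule is applied for patients with low bodyweight to avoid exceeding blood draw volume limits". Section 7.5.1.14 adds a fallback: "Should the blood volume be restricted at any of the sampling time points, then the analyses should be prioritized in the following order". That list ranks ADA first, then coagulation, PK, hematology, chemistry and HS, with the two future-research samples last.

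Appendix 1 gives the volumes. Table 12 lists them by study week and weight band. Table 13, "Blood sampling volumes (mL) per 4-week study periods", groups them into Weeks -1 to 3, 4 to 7, 8 to 11 and so on. Its largest entry at 10 to <15 kg is 23.6 mL.

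**The concern.** The limit applies to any period of 4 weeks, whereas Table 13 tests one fixed set of blocks. Sampling is densest in Weeks 1-4: six safety panels, two ADA samples, three HS samples and the first two PK profiles. The break between Weeks 3 and 4 splits that stretch. A reader who sets 23.6 mL against 24.0 mL at 10 kg concludes that the low-weight schedule complies.

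If it does not, the lightest eligible children are affected, and a child of that weight is the protocol's own reference case. Protocol 7.1 also steers enrolment toward them: "Patients are assigned to a dose cohort in consecutive order as the eligibility criteria have been confirmed, with prioritization of the younger patients". Compliance then depends on each site adding up Table 12 across the block boundary and deciding for itself what to omit. Sites could omit different samples, in the weeks that feed the Safety Review Committee's escalation decision.

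**Working it through.** **Inputs.** Limit and mL/kg: Protocol 7.5.1.14 and Table 7. Weekly volumes: Table 12. PK sample counts: Table 6, at 0.3 mL each (7.5.6.1). Infusion window: 7.4.6.

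**1. Limit.** 0.03 x 80 = 2.4 mL/kg, i.e. 24.0 mL at 10 kg, 36.0 mL at 15 kg and 48.0 mL at 20 kg. These match Table 7.

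**2. Table 13 reproduced.** At 10 to <15 kg, Weeks -1 to 3: 2.1 + 8.0 + 9.5 + 4.0 = 23.6 mL. Weeks 4 to 7: 7.3 + 4.0 + 3.7 + 3.7 = 18.7 mL. All six blocks reproduce in all three weight columns, as do the study totals of 121.4, 119.9 and 108.1 mL.

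**3. Weeks 1-4 at 10 to <15 kg.**
- Week 1: safety 7.4 + PK 0.6 = 8.0
- Week 2: safety 7.4 + ADA 1.5 + HS 0.3 + PK 0.3 = 9.5
- Week 3: safety 3.7 + HS 0.3 = 4.0
- Week 4: safety 3.7 + ADA 1.5 + HS 0.3 + PK 1.8 = 7.3
- Sum = 28.8 mL; 28.8 / 2.4 = 12.0 kg

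The reduced PK schedule and the omitted Week 3 Day 3 panel are already in these figures. As a share of blood volume, the total is 28.8/800 = 3.6% at 10 kg (4.8 mL, or 20%, over), 28.8/880 = 3.3% at 11 kg and 28.8/960 = 3.0% at 12 kg.

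**4. Does it fit in 4 weeks?** Yes. Table 12 counts the Week 4 168 h sample in Week 5. The last Week 4 draw in this band is at 96 h (Day 5), which is treatment Day 21 + 5 = 26.

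**5. Can PK adjustment cure it?** PK in Weeks 1-4 is 0.6 + 0.3 + 0 + 1.8 = 2.7 mL. Without any PK, 28.8 - 2.7 = 26.1 mL, and 26.1 / 2.4 = about 10.9 kg. Below that weight it cannot. At 15 to <20 kg the excess at 15 kg is 37.0 - 36.0 = 1.0 mL, against 1.8 + 0.9 + 0.9 + 3.6 = 7.2 mL of PK, so dropping some PK samples is enough on nominal timing.

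**6. Visit window.** From the fifth infusion a window of +/-1 day applies, so that infusion can fall on Day 28. Its pre-infusion draw is 3.7 + 0.3 = 4.0 mL.

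| Band | Weeks 1-4 (mL) | Limit at bottom of band (mL) | Over below | With fifth infusion on Day 28 (mL) | Over below |
|---|---|---|---|---|---|
| 10 to <15 kg | 28.8 | 24.0 | 12.0 kg | 32.8 | about 13.7 kg |
| 15 to <20 kg | 9.2 + 10.1 + 8.6 + 9.1 = 37.0 | 36.0 | about 15.4 kg | 41.0 | about 17.1 kg |
| >=20 kg | 10.7 + 10.1 + 8.6 + 9.1 = 38.5 | 48.0 | not over | 42.5 | not over |

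**7. Next whole-week run.** Weeks 2-5 at 10 to <15 kg: 9.5 + 4.0 + 7.3 + 4.0 = 24.8 mL, over below 24.8 / 2.4 = about 10.3 kg.

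**8. Updated PK schedule.** SAP Table 7 adds a 72 h sample at Week 4 for >=10 kg, and at Weeks 1 and 4 for >=15 kg. If it is drawn in addition to the 96 h sample (an assumption), the Weeks 1-4 totals rise to 28.8 + 0.3 = 29.1 mL and 37.0 + 0.6 = 37.6 mL.

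**The case against.** The strongest reply is that the protocol already governs this. It states the limit, tabulates it by weight, says PK will be adjusted to respect it and ranks the analyses to keep when volume is short. Appendix 1 is only an overview, and the operative volumes are in a Laboratory Manual that is not available here. The rule is also worded as a recommendation. All of this stands against the reading that any site following the protocol must breach the limit. It does not rescue Table 13: the priority list says what to drop once volume is restricted, but nothing in Appendix 1 shows that Weeks 1-4 need a restriction. The statement that the reduced PK schedule avoids the limit is also wrong, as written, for the lightest children.

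A second reply is that the practical stakes are small. SAP 4.1 says that Cohort 3 will not start and that all six included children have entered the extension, so no sampling in this study can change. No endpoint or analysis depends on Table 13. Protocol 5.1.1 says diagnosis usually comes in a phase that starts around 3 to 4 years, so children near 10 kg may be few. This stands, and it limits the remaining action to a corrected table and a retrospective check.

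Two stronger inferences are tempting. One is that Table 13 contains an addition error. It does not; the fault is the choice of window. The other is that enrolled children were over-sampled. The documents give neither their weights nor the volumes drawn, and samples may have been omitted.

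**Conclusion.** The point holds as a defect in the compliance check and should be fixed. The planned schedule exceeds the protocol's own 4-week limit in Weeks 1-4 for children of 10 to <12 kg, by up to 4.8 mL, and PK adjustment alone cannot cure this below about 10.9 kg. At 15 to about 15.4 kg the excess is at most 1.0 mL and can be cured by dropping some PK samples on nominal timing. An early fifth infusion widens the affected ranges to about 13.7 kg and 17.1 kg. At >=20 kg there is no problem.

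This rests on the nominal volumes in Table 12, on 80 mL/kg, and on reading the limit as applying to any 28 days. It also assumes that the separate 8.4 mL Baseline draw is taken at least 4 weeks before the first infusion, which the protocol asks for only when possible. The Laboratory Manual and the clarification letters cited in SAP section 17 were not available. The SAP's schedule keeps the same safety panels in Weeks 1-4.

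**What to change.** - Replace Table 13 with the maximum volume over any rolling 28 days, by weight. Allow for the visit window and the current PK schedule, including the SAP's 72 h sample if it is drawn as well as the 96 h sample. Runs of whole weeks are not enough, because they miss a fifth infusion on Day 28.
- State at which weights Weeks 1-4 need a cut, and have the sponsor pre-specify that cut using the 7.5.1.14 priority list. Which samples go is the sponsor's trade-off: the Safety Review Committee uses safety laboratory, PK and HS data from these weeks, so no particular cut is prescribed here.
- For the six included children, compare the maximum rolling 28-day volume with 2.4 mL/kg and report any excess or omitted samples. Use nominal volumes for the samples taken if drawn volumes were not recorded.

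The cost is a corrected table and a short retrospective check. If the schedule is reused, the lightest children would have a few fewer low-priority samples.
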